1.0 Study Summary

Study Title	Ultrasonographic evaluation of gastric volume and contents before surgery in children
Study Design	Prospective, non-blinded observational study
Primary Objective	The primary objective of this study is to evaluate gastric volume and contents in patients who are scheduled for elective, urgent, and emergent surgery
Secondary Objective(s)	None
Research Intervention(s)/ Investigational Agent(s)	There will be no change in anesthetic management or use of investigational agents.
IND/IDE #	Not applicable
Study Population	Patients who are scheduled for elective, urgent or emergent surgery
Sample Size	300 (100 in each group)
Study Duration for individual participants	Less than 10 minutes
Study Specific Abbreviations/ Definitions	CSA=cross sectional area POCUS=Point-of-Care Ultrasound RSI=Rapid Sequence Induction RLD=right lateral decubitus

2.0 Objectives

- 2.1 The primary objective of this study is to evaluate gastric volume and contents as well as gall bladder size in patients scheduled for routine, urgent, and emergency surgery.
- 2.2 The hypothesis is that patients with stress, pain and opioid administration will have delayed gastric emptying and therefore a larger gastric fluid volume than those scheduled for elective surgery. The patients who have an appropriate NPO time will have a larger gallbladder size than the patients with shorter NPO time.

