3.0 Background

- 3.1 Point-of-Care Ultrasonography (POCUS) has been recognized as a powerful tool to evaluate critically ill patients. Using gastric ultrasonography, we can evaluate gastric volume and the types of contents as well as gall bladder size. The cross-sectional area of the gastric antrum is used to calculate the gastric volume. The full stomach state in pediatric patients scheduled for elective surgery is low at only 0-1%. However, it is unknown how lack of appropriate NPO time affects gastric volume and contents as well as gall bladder size. The gallbladder stores bile and starts to empty after the presence of fatty food in duodenum. Gallbladder emptying also

requires relaxation of the sphincter of Oddi, which may be disturbed by opioids. Therefore, it may be useful to evaluate patient NPO status. The diameter of great vessels has been used to evaluate patient volume status in pediatric patients.

- 3.2 Point-of-care gastric ultrasound had a sensitivity of 1.0 and a specificity of 0.975 to detect a “full stomach”. ¹ Using point-of-care gastric ultrasound, a previous study reported that 0-1 % of the healthy pediatric patients scheduled for elective surgery were at risk of pulmonary aspiration ^{2 3} However, 35 % of the adult patients scheduled for unplanned surgery had a full stomach even after ≥ 6 hours of NPO time ⁴ The normal gallbladder sizes in healthy children has been evaluated after fasting in previous report. ⁵ There is no article which reports the relationship between NPO state and gallbladder size.
- 3.3 Rapid sequence induction (RSI) is widely used to avoid pulmonary aspiration during anesthetic induction. However, RSI is the risk factor for oxygen desaturation and other airway complications when compared to standard anesthetic induction techniques. The current study will help identify which trauma patients are truly at risk for aspiration and therefore require RSI.

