4.0 Study Endpoints

- 4.1 The primary study endpoint is the number (percentage) of patients in the urgent, emergent group with a full stomach state as assessed by gastric volume and contents despite an appropriate NPO time.
- 4.2 The secondary endpoint will be to determine gall bladder size between fasted patients undergoing elective versus urgent/emergent surgery. The other endpoint will be to evaluate the preoperative volume status.

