6.0 Procedures Involved*

6.1 This is a prospective observational study that will be conducted in 300 patients, ranging in age from 2 to 18 years who are scheduled for routine, urgent or emergent surgeries. There will be no change in clinical practice regarding choice of anesthetic technique as a result of this research study. Before surgery in the pre-operating area, the ultrasonographer will evaluate the gallbladder size and volume. Procedure time will be recorded for the ultrasonography. Demographic data, including age, sex, height, weight, nil per os time, preoperative symptoms, administered opioids, and types of the surgery will be recorded.

6.2

Ultrasound protocol

All ultrasound scans will be performed by study investigators by using Sonosite X-porte (Sonosite Inc. USA) machine and 3-8 MHz curved linear probe with abdominal setting. The investigators have enough experiences of POCUS.

All patients will be lying supine, followed by RLD position. Patients were placed in the supine position, followed by the right-lateral decubitus (RLD) position. In cases where it is not feasible to place the patient in the right lateral decubitus position, the patient can be placed in a 45 degree head up position with a bump placed under the left hip. The gastric antrum is identified in a sagittal plane between the left lobe of the liver and the pancreas at the level of the descending aorta and supra mesenteric artery or inferior vena cava, as previously reported.⁶ One video clip will be recorded for each patient in the supine and RLD positions. The qualitative measurements (empty versus nonempty) will be reported to the attending anesthesiologist. The quantitative measurements will be performed at later time. The quantitative exam is performed using the cross-sectional area of the gastric antrum. The CSA of the antrum will be measured with a free-tracing method to follow the outer margin of the antrum corresponding to the serosa.⁷ The gastric volume will be calculated using the following formula.⁸

$$\text{Gastric volume (ml.kg}^{-1}\text{)} = [-7.8 + 0.035 \times \text{CSA (mm}^2\text{)} + 0.127 \times \text{age (months)}]/\text{body weight (kg)}.$$

The qualitative measurements will be performed using 3-point grading scale.⁹

Grade 0: no fluid visible in the antrum in either the supine or RLD position.

Grade 1: antral fluid visualized only in the RLD position.

Grade 2: antral fluid visualized in both the supine and RLD position.

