12.0 Local Number of Subjects

12.1 300 (100 in each group of routine, urgent, and emergent cases).

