17.0 Data Management* and Confidentiality

- 17.1* Summary statistics will be described by using means and standard deviation for parametric variables and median with interquartile ranges (IQRs) for nonparametric variables. The Kolmogorov-Smirnov test will be used to assess the normality of data. Bivariate analysis for paired continuous variables will be conducted using the paired t test and Wilcoxon signed-rank test, and for independent continuous variables it is conducted using the independent samples t-test and Wilcoxon rank-sum test. Bivariate analysis for categorical variables will be conducted using the Chi-square test or Fisher's exact test, where appropriate. P value less than 0.05 is considered to indicate statistical significance. Statistical analysis will be done using SAS 9.4 and G*Power version 3.1.9.2.

Primary Outcome: The primary outcome is the proportion of full stomach state.

- 17.2* Research records will be stored in a locked cabinet and password protected computer. Only certified research personnel will be given access to identifiable subject information
- 17.3* Following publication of study results, research records will be stored for a period of 3-5 years and then will be destroyed by placing in a secure shredding bin.

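### Opioid and onset times are not collected and no analysis splits by opioid use, so the gallbladder comparisons are open to confounding and the full-stomach percentage cannot show in whom fasting fails

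*Combined protocol and SAP*

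**What the plan says.** All references are to the combined protocol and SAP.

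- **Stomach (2.2).** The hypothesis is that "patients with stress, pain and opioid administration will have delayed gastric emptying and therefore a larger gastric fluid volume" than elective patients.
- **Gallbladder (2.2, 3.1).** Section 2.2 predicts a larger gallbladder after an appropriate fast than after a shorter one. Section 3.1 adds that emptying "requires relaxation of the sphincter of Oddi, which may be disturbed by opioids".
- **Endpoints (4.1, 4.2).** The primary endpoint is the percentage of urgent and emergent patients with a full stomach "despite an appropriate NPO time". The secondary endpoint compares gallbladder size in fasted elective and fasted urgent/emergent patients.
- **Data (6.1, repeated in 6.2).** Besides basic demographics, "nil per os time, preoperative symptoms, administered opioids, and types of the surgery will be recorded". No time of injury or symptom onset and no time of opioid dosing is listed.
- **Analysis (17.1).** Only bivariate tests are described. Nothing is stratified by, or adjusted for, opioid use or timing.
- **Purpose (3.3).** The study is meant to help identify which trauma patients are really at risk of aspiration.

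**The concern.** If pain, stress or opioids slow emptying, an hour of fasting before they begin is not worth the same as an hour after. A child hurt 1 h after a meal and a child hurt 7 h after a meal, both scanned at 8 h, have the same recorded NPO time. On the plan's own hypothesis they have had quite different opportunity to empty. The listed data cannot tell them apart, so a pooled percentage cannot answer the question in 3.3 about which patients are at risk.

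The gallbladder comparisons have a further difficulty. Section 3.1 names opioids as something that may alter gallbladder emptying whatever the fasting time. If opioid use differs between the groups compared, a difference in size, or the lack of one, cannot be put down to fasting or to urgency of surgery. Section 17.1 has no step that would separate the two.

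**Working it through.** The documents give no figure that tests this point. The sample size, "300 (100 in each group of routine, urgent, and emergent cases"), has no stated derivation and does not bear on it. The check is therefore a comparison of passages, followed by illustrations whose assumed inputs are marked.

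**1. What the listed data can separate.** The mechanism in 2.2 needs the interval from last intake to the start of pain or opioid. Sections 6.1 and 6.2 give total NPO time and which opioids were given. Opioid use as yes/no is available; the interval is not.

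**2. Equal NPO hours, unequal emptying.** Assume emptying at half speed after onset. Effective hours = hours before onset + 0.5 × hours after onset.
- Onset at 1 h, scan at 8 h: 1 + 0.5 × 7 = 4.5 h.
- Onset at 7 h, scan at 8 h: 7 + 0.5 × 1 = 7.5 h.

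**3. Effect on the pooled primary percentage.** Let f be the share of urgent/emergent children with early onset, q1 their full-stomach risk and q0 the risk in the rest. Pooled percentage = f × q1 + (1 − f) × q0.

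Section 3.2 supplies two rates: "0-1 % of the healthy pediatric patients scheduled for elective surgery were at risk of pulmonary aspiration", and 35% of adults having unplanned surgery had a full stomach after at least 6 h. Using 1% for q0 and 35% for q1 is an assumption.

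| f | Calculation | Pooled |
|---|---|---|
| 25% | 0.25 × 35 + 0.75 × 1 | 9.5% |
| 50% | 0.50 × 35 + 0.50 × 1 | 18.0% |
| 75% | 0.75 × 35 + 0.25 × 1 | 26.5% |

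If q0 = q1 = 35%, the result is 35% for every f. The plan collects nothing that would show which situation applies.

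**4. Gallbladder size by NPO time (2.2).** Let D be the true difference (appropriate minus shorter NPO) without opioids, oA and oS the opioid shares in the two groups, and dA and dS the opioid's effect on size in each. Observed difference = D + oA × dA − oS × dS.
- Assume D = 60% of volume, no effect in the appropriately fasted (dA = 0), and complete prevention of the feeding effect in opioid-treated short-NPO children (dS = D). The observed difference is 60% × (1 − oS): 42% for oS = 30% and 18% for oS = 70%.
- If oA × dA exceeds oS × dS, the observed difference is larger than D.

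The documents give none of these quantities, so neither size nor direction is known.

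**5. Gallbladder size, elective versus urgent/emergent (4.2).** By the same algebra, with opioid shares oU and oE and a common opioid effect d, the observed difference is the true one plus (oU − oE) × d. It is free of opioid influence only if the shares are equal or d is zero.

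**6. Precision of a split table.** If all 100 + 100 = 200 urgent and emergent children met the NPO requirement, the 95% half-width around 35% is 1.96 × √(0.35 × 0.65 / n): 6.6 points for n = 200, 9.3 for n = 100 and 13.2 for n = 50. That is adequate for a descriptive table.

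**The case against.** A reader might infer that the fasting-based endpoints are misclassified. The documents do not support that. Full stomach is read from the scan (6.2), and NPO time is naturally read as clock time since intake. A child with a full stomach after a long fast is correctly classified on both counts, and that event is what the study sets out to find. The two 8 h children show heterogeneity within a class, not membership of the wrong class.

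Three other strong readings also fail.
- **Counting rule.** The plan does not say that NPO time is counted through injury or opioid dosing; it states no counting rule at all. Nor does it name injury as slowing emptying. It names stress, pain and opioids for the stomach, as a hypothesis, and opioids for the gallbladder, with a may. Onset time is a proxy.
- **Diluted opioid exposure.** One might argue that doses given just before the scan dilute an exposed group. No opioid-exposed group is planned, so there is no such analysis to correct.
- **Bias toward no difference.** This requires short-NPO children to receive more opioids. The documents do not say so.

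It is also fair that a recently fed child lies outside the 4.2 comparison, that a yes/no opioid split is already possible, and that the documents describe using Epic to find patients, not to obtain onset times. A related gap, that appropriate NPO time and fasted have no hours threshold, needs no physiological assumption to show.

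What remains is that the yes/no split is not planned, 4.2 can still be confounded by opioid use among fasted children, and the intake-to-onset interval cannot be reconstructed from the listed fields.

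**Conclusion.** The point holds as one of confounding and interpretability. The primary percentage stands as a description of the enrolled urgent and emergent children, but it cannot show in which trauma patients an appropriate fast fails. The gallbladder comparisons in 2.2 and 4.2, run as written, are open to confounding by a factor the plan itself names.

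The size is not known from the documents. The 9.5% to 26.5% range rests on assumed risks, one taken from adults, and on all 200 children meeting an NPO requirement that is not quantified. The 42% and 18% figures rest wholly on assumptions. If the interval has no effect, the pooled figure loses nothing and the added table would show it. This is a worthwhile, inexpensive improvement and not a flaw that invalidates the study.

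**What to change.** 1. **Section 17.1, gallbladder.** Make the comparison by NPO time first in children with no opioid between last intake and scan, and show opioid-treated children separately. Split the 4.2 elective versus urgent/emergent comparison by opioid use in the same way. A yes/no split is possible from data already listed.
2. **Section 6.1, data.** Add time of last intake, time of injury or symptom onset where known, and time of first opioid dose.
3. **Section 17.1, stomach.** For urgent/emergent children, report full stomach and gastric volume by last-intake-to-onset interval alongside total NPO time, as a secondary, descriptive table. Leave the primary endpoint unchanged and report how many onset times are missing.

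**Cost.** Three time fields and a few lines of text. Onset time will be approximate or missing for some children with non-trauma illness, so it is best asked at enrolment. The opioid-free gallbladder comparison uses fewer children and loses some precision. The split deals with opioids only; other differences between elective and unplanned patients remain.

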“Full stomach is defined by the visualization of solid contents or frost-grass pattern and/or by a calculated gastric fluid volume $>1.5 \text{ ml.kg}^{-1}$.

The gallbladder size and volume will be evaluated as previously reported.⁵

The gallbladder volume was calculated as following formula.

Volume = $0.52 \times L$ (the greatest length) $\times W$ (anterior posterior dimension) $\times W$ (transverse width)

B and C are assumed to be equal.

[figure not shown]

FIGURE 1. Method of sonographic measurement of gallbladders. The gallbladder volume was measured using the prolate ellipsoid volume formula: $V = 0.52 \times L \times W \times W$. A is the greatest length (L), B is the anteroposterior dimension (W) and C is the transverse width (W). B and C were assumed to be equal.

The diameter of great vessels will be measured in supine position.

Demographic data, including age, sex, height, weight, nil per os time, preoperative symptoms, administered opioids, and types of the surgery will be recorded.

6.3 There are no foreseeable risks associated with the use of ultrasound.

6.4

Ultrasound data will be stored in the ultrasound machine. The research team will transmit the data to the password-secured server and store as MP4 file and JPEG file. The data will then be deleted from the ultrasound machine.

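### Gallbladder hypothesis 2.2 treats fasting time as two undefined classes and section 17.1 offers only group tests, although fasting time is recorded and gallbladder volume is continuous

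*Combined protocol and SAP*

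**What the plan says.** - **Hypothesis (2.2).** "The patients who have an appropriate NPO time will have a larger gallbladder size than the patients with shorter NPO time". Neither class is defined in hours here or anywhere else. The only fasting duration in hours, at least 6, is in section 3.2 and describes a cited study in adults.
- **Data (6.1, repeated in 6.2).** For each child, "nil per os time, preoperative symptoms, administered opioids, and types of the surgery will be recorded", along with age, sex, height and weight. Section 6.2 computes gallbladder volume from length and width, so the outcome is continuous.
- **Analysis (17.1).** The only statistical text says that "for independent continuous variables it is conducted using the independent samples t-test and Wilcoxon rank-sum test". For categorical data it names chi-square or Fisher's exact test. No correlation, regression or other model appears in the document.
- **Endpoint (4.2).** "The secondary endpoint will be to determine gall bladder size between fasted patients undergoing elective versus urgent/emergent surgery". This compares surgery groups among fasted children, not children with different fasting times.
- **Stated gap (3.2).** "There is no article which reports the relationship between NPO state and gallbladder size".

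**The concern.** Both variables needed for an analysis by hours are collected, yet the hypothesis uses one of them only as two classes and the analysis section has no method that could use hours. Under a two-class test, a child well below the cut and one just below it count as the same, while two children just either side of it count as opposites. Because the cut is not stated, it could also be chosen after the data are seen.

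Two things are at stake for this hypothesis. One is power, if the association is weak to moderate. The other is any description of how gallbladder size changes with fasting time, which the plan says nobody has reported. In addition, 4.2 is restricted to fasted children, so no listed endpoint tests 2.2.

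**Working it through.** **Inputs from the documents:** 300 children, 100 per group (1.0, 12.1); significance at 0.05 (17.1; two-sided assumed). The plan gives no power, effect size or SD, and does not tie 300 to this hypothesis, so there is no planned figure to reproduce.

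**Assumed:** the distribution of hours, the share *p* in the shorter class, the correlation *r*, and the shape of the curve. Cuts at 6 h and 8 h are illustrations only, not proposals.

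**1. Linear relation, normal hours.** Information kept by the split = φ(z_p)² / [p(1−p)]:
- p = 0.5: 0.3989² / 0.25 = 0.637; 300 children count as 191
- p = 0.2: 0.2800² / 0.16 = 0.490; 147
- p = 0.1: 0.1755² / 0.09 = 0.342; 103

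A test with 80% power on hours has Φ(2.80 × √kept − 1.96) after the split:
- 2.80 × 0.798 − 1.96 = 0.27, power 61%
- 2.80 × 0.700 − 1.96 = 0.00, power 50%
- 2.80 × 0.585 − 1.96 = −0.32, power 37%

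A joint 2-df spline test in the same setting (noncentral chi-square, noncentrality 2.80² = 7.84, critical value 5.99) has about 71%. It pays for the extra degree of freedom but stays above the split.

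**2. Dependence on the strength of association, N = 300.** Power = Φ(atanh(r) × √297 − 1.96), with r replaced by r × √kept for the split:

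| r | hours, linear | split 50/50 | split 80/20 | split 90/10 |
|---|---|---|---|---|
| 0.15 | 74% | 55% | 44% | 33% |
| 0.20 | 94% | 79% | 68% | 53% |
| 0.30 | >99% | 99% | 96% | 86% |

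**3. Linear relation, other distributions (simulation).** With hours uniform on 2–16 h, the split loses 27–39%. With skewed hours (lognormal, median 10 h, log SD 0.5; gamma, shape 4, mean 10 h), it loses 47–78%.

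**4. Gallbladder size rises, then is flat from the cut onward.** Share of the variation in the true curve captured (spline knots at the 10th, 50th and 90th percentiles of hours):

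| hours | cut and plateau | split | straight line | 3-knot spline |
|---|---|---|---|---|
| uniform | 6 h | 0.682 | 0.536 | 0.881 |
| uniform | 8 h | 0.631 | 0.725 | 0.985 |
| gamma | 6 h | 0.611 | 0.293 | 0.714 |
| gamma | 8 h | 0.580 | 0.474 | 0.929 |
| lognormal | 6 h | 0.618 | 0.162 | 0.510 |
| lognormal | 8 h | 0.601 | 0.318 | 0.816 |

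The split beats the line in five of six rows. The spline beats the split in five of six; the exception is the most skewed distribution with the smallest shorter class (15%).

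**5. Power in the rows of step 4.** Let the true curve explain 4% of the variance of log volume (r = 0.20) and use F tests with N = 300. Split against 2-df spline, in table order: 82% v 85%, 79% v 89%, 78% v 76%, 76% v 87%, 78% v 60%, 77% v 82%. If the truth is instead a step exactly at the cut, the split has 94% and the spline 67–82% across these distributions.

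All these figures are unadjusted. Adjustment for surgery group would reduce the usable variation in fasting time for either analysis.

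**The case against.** The strongest reply is that the size of the loss depends on inputs the documents do not supply, and that even its direction is not fixed. Section 3.1 describes emptying after fatty food, which gives no support for a straight rise over all hours. Step 4 shows that a straight-line test can do worse than the split. This stands, and it is why the test should use a spline rather than a linear term.

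A reader might infer that the plan throws away between a third and two thirds of its information, or that a split is harmless only under an exact step. The documents support neither. The first needs linearity and normal hours. The second fails when the alternative is a straight line, and one row of step 4 shows that it can fail against a spline too. Nor do the documents show that the shorter class will be small: 200 of the 300 children are urgent or emergent cases, so the 80/20 and 90/10 figures are scenarios.

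It is also fair to say that 17.1 is a general list tied to no hypothesis, that recorded hours are not lost and could be analysed later, and that telling fasted from unfasted children is a two-state question for which the contrast remains useful. These points limit the severity. They do not supply a prespecified test of 2.2, a cut-point, or any method that uses hours.

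**Conclusion.** The point holds in conditional form. On the text, 2.2 is framed in two undefined classes, 17.1 lists only group tests, and the recorded fasting time has no planned use on its own scale. On size, the split keeps 64%, 49% or 34% of the information at 50/50, 80/20 or 90/10 if the relation is linear and hours are normal. Under a plateau it can beat a straight line but generally captures less of the curve than a spline.

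The effect on power matters for weak to moderate associations. At r = 0.30 or more, the split keeps at least 86% power with 300 children even at 90/10, although the shape of the relation would still go unestimated.

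This is a worthwhile, inexpensive improvement to the gallbladder hypothesis. A reader might take it as a threat to the main result; it is not, because the primary outcome is the proportion with a full stomach.

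**What to change.** In 17.1:
- Make the test of the 2.2 fasting hypothesis a regression of log gallbladder volume on nil per os hours, entered as a 3-knot restricted cubic spline with knot percentiles fixed in advance, in all children scanned. Report the joint 2-df test and show the fitted curve with its confidence band.
- Adjust for age or weight, opioid administration and surgery group, all already recorded. Section 3.1 itself says opioids may disturb gallbladder emptying, and ages run from 2 to 18 years.
- Keep appropriate versus shorter as a descriptive contrast, with the sponsor's definition of the classes written down before the data are examined.
- State that the 4.2 comparison, restricted to fasted children, is separate and does not test 2.2.

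**Cost:** wording only, with no new data or patients. The extra degree of freedom costs some power if the relation is truly linear (80% becomes about 71%; at r = 0.20 with 300 children, 94% becomes 89%) and more if it is a step exactly at the cut (94% becomes 67–82% in step 5). The log scale needs a positive volume, so 17.1 should also say how a gallbladder that cannot be measured is handled.
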